4.2 STUDY DESIGN

Single center, randomized, double-blind placebo controlled clinical trial of pirfenidone for the attenuation of progression of fSAD in lung transplant recipients with CLAD. A total of 60 patients will be enrolled in the trial.

Eligible patients will be randomized 1:1 to receive either pirfenidone 801 mg TID or placebo.

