4.4 EXCLUSION CRITERIA

- Acute Rejection (AR) diagnosis by biopsy in the 28 days prior to enrollment
- Treatment with pulse steroids, Anti-thymocyte Globulin (ATG), extracorporeal photopheresis (ECP), plasmapheresis, or Immunoglobulin therapy aimed at CLAD within the 28 days prior to enrollment
- If the subject is receiving chronic Azithromycin therapy, the dose must be stable for the 28 days prior to enrollment
- Presence of active pulmonary infection at the time of enrollment as determined by an investigator in consultation with the treating pulmonologist
- Diagnosis of bronchial stenosis either a) requiring stenting, or b) thought to be responsible for the spirometric decline by principal investigator
- Abnormal liver function tests (AST or ALT > 2 x upper limit of normal (ULN), Alkaline phosphatase > 2.5 x ULN, total bilirubin > ULN) or known cirrhosis (>2 times upper limit of normal of AST/ALT/AP)
- Total WBC < 3.0 K/uL
- Moderate to Severe Renal insufficiency (CrCl <15 mL/min calculated by the Cockcroft-Gault equation)

- Use of any medication known to cause significant interactions with pirfenidone (strong CYP1A2 inhibitors such as Fluvoxamine or Enoxacin or inducers)
- Pregnancy or lactation. Women of child-bearing potential will have a pregnancy test at enrollment and must agree to maintain highly effective contraception with two methods of birth control from the date of consent through the end of the study.
- Tobacco use within 6 months
- History of alcohol abuse in the past 1 year as determined by the treating pulmonologist
- Any condition other than CLAD that will likely result in death in the next 1 year
- Any condition in the judgement of the principal investigator that would preclude participation in this study
- EKG with QTc interval > 500 msec at screening
- Listed for repeat lung transplantation

Excluded therapies:

The following therapies are not permitted during the study:

- Investigational therapy, enrollment in another therapeutic clinical trial within 30 days or 5 half-lives of study medication (whichever is longer)
- Fluvoxamine

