5.2 Baseline Assessment (Visit 1, Week 0)

At the time of baseline, the coordinator will document the following:

- Vital signs (weight, temperature, blood pressure, heart rate, respiratory rate, pulse oximetry)
- Physical exam including general appearance, HEENT, cardiovascular, pulmonary, abdominal, neurologic, dermatologic, and musculoskeletal exams
- Current medications
- Safety blood work for renal and liver evaluation
 - AST, ALT, AP, total bilirubin, creatinine
- Review bronchoscopy results (if performed)
- ECG
- Perform spirometry
- Undergo an HRCT scan with inspiratory and expiratory image acquisition (if HRCT was not done in preceding 6 weeks)
- Serum pregnancy test (if applicable)
- Review adverse events

5.3 Visits 2, 3, 5, 6 (Weeks 4, 8, 16, 20): may be performed at study center or by local lab draw in conjunction with phone visit

- Safety labs to monitor renal and liver function AP, ALT, AST, total bilirubin, creatinine
- Review hospitalizations
- Review medication compliance
- Review concomitant medications
- Review adverse events

5.4 Visit 4 (Week 12):

- Vital Signs (weight, temperature, blood pressure, heart rate, respiratory rate, pulse oximetry)
- Physical exam including general appearance, HEENT, cardiovascular, pulmonary, abdominal, neurologic, dermatologic, and musculoskeletal exams
- Safety blood work for renal and liver evaluation
 - o AP, ALT, AST, total bilirubin, creatinine
- Spirometry
- ECG
- Review hospitalizations
- Review medication adherence
- Review concomitant medications
- Review adverse events
- 5.5 Visit 7 (Week 24):
 - Vital Signs (weight, temperature, blood pressure, heart rate, respiratory rate, pulse oximetry)
 - Physical exam including general appearance, HEENT, cardiovascular, pulmonary, abdominal, neurologic, dermatologic, and musculoskeletal exams Safety blood work for renal and liver evaluation

- o AP, ALT, AST, total bilirubin, creatinine
- Spirometry
- ECG
- HRCT scan
- Review hospitalizations
- Review medication adherence
- Review concomitant medications
- Review adverse events
- Collect unused study medication and return to investigational pharmacy
- Bronchoscopy with consent of patient and primary physician if no contraindication identified

5.6 Visit 8 (Week 28) (Phone visit):

At the 28 week phone visit, the coordinator will:

- Review hospitalizations
- Review adverse events
- Collect vital status

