6. RECRUITMENT

University of Michigan has in place a unique prospectively collected dataset of lung transplant patients (Organ Transplantation Information System (OTIS) database). We have, as a part of this database, devised a system in which every patient's baseline lung function post-transplant is analyzed to generate their baseline FEV1 as well as their CLAD status. The trial's study team will screen lung transplant patients using this program to identify potential subjects.

We have run this profile once to determine if recruitment of 60 CLAD patients is viable in the planned two years. At present among all alive patients with lung transplant at our center, 92 patients meet spirometric criterion for CLAD. Phenotype and grade distribution are shown below:

* CLAD grade is based on ISHLT definition. The study plans to include all patients with diagnosis of CLAD irrespective of the stage. Fibroproliferative remodeling in a transplanted lung is an ongoing event as evidenced by continued progressive decline in lung function, worsening of small airway obstruction, and evidence of change in the phenotype of mesenchymal cells isolated from BAL of these patients. It is important that an anti-fibrotic agent be effective at all stages of CLAD because patients can present in any stage of CLAD at the very disease onset. Furthermore, CLAD becomes a chronic disease and patients can survive for prolonged periods of time after onset of CLAD. Hence, the ability of an antifibrotic agent to halt fibroproliferation at various time points after onset of CLAD is of key significance.

^A CLAD is identified by decline in FEV1 below 80% of post-transplant baseline as per ISHLT definition. Our published work has shown that patients can present either as an isolated decline in FEV1 (BOS) or as a concurrent decline in both FEV1 and FVC, also termed restrictive allograft syndrome (RAS).¹⁰ As both of these presentations arise from fibrosis, we will not limit our study to one specific phenotype.

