8. DRUG DOSAGE & ADMINISTRATION

Dosage and Administration

	Pirfenidone	Placebo
Substance	Pirfenidone	-
Pharmaceutical formulation	Capsule	Capsule
Source	Genentech	Genentech
Unit strength	267 mg	267 mg
Route	Oral	Oral
Dosage		
Days 1 through 7	267 mg three times daily	267 mg three times daily
Days 8 through14	534 mg three times daily	534 mg three times daily
Days 15 onward	801 mg three times daily	801 mg three times daily

- Take with food.
- Upon initiation of treatment, titrate to the full dosage of 2403 mg/day over a 14-day period as above.

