8.1 Adverse reactions

The most common adverse reactions (≥10%) are liver problems, photosensitivity, rash, abdominal pain, nausea, vomiting, diarrhea, dyspepsia, fatigue, headache, dizziness, anorexia, sinusitis, insomnia, weight loss, and arthralgia. These possible adverse events are documented in the informed consent.

Management of abnormal liver function tests

Elevated ALT, AST, and bilirubin elevations have occurred with pirfenidone and will be monitored monthly as above. The investigator will monitor patients for toxicities.

The following protocol will be followed for management of elevation in AST, ALT, and total bilirubin:

Magnitude of AST or ALT elevation	Recommendation
3 to 5 x ULN	Confounding medications should be discontinued if clinically indicated, other causes excluded, and the patient monitored closely. The dose of study treatment may be reduced or interrupted if clinically appropriate, with subsequent repeat titration to full dose, as tolerated
≤5 x ULN accompanied by symptoms or hyperbilirubinemia (>2x ULN)	Study treatment should be permanently discontinued
>5 x ULN	Study treatment should be permanently discontinued

Management of photosensitivity and rash

Photosensitivity and rash have been noted with pirfenidone. Patients will be instructed to avoid exposure to sunlight and sunlamps. Patients will be instructed to wear sunscreen (sun

protection factor 50 or higher) and protective clothing daily. Temporary dosage reductions or discontinuations may be required.

If a patient experiences significant rash or photosensitivity, treatment of symptoms and/or temporary dose reductions, interruptions, or discontinuation of study treatment should be considered.

Management of gastrointestinal disorders

Nausea, vomiting, diarrhea, dyspepsia, gastroesophageal reflux disease, and abdominal pain have occurred with pirfenidone. Temporary dosage reductions or discontinuations may be required.

Dosage Modification due to Drug Interactions

Ciprofloxacin is a moderate CYP1A2 inhibitor. With the use of ciprofloxacin at a dosage of 750 mg twice daily, reduce pirfenidone to 534 mg three times a day (1602 mg/day).

EKG abnormalities

If the QTc interval is > 550 msec, this should be confirmed with a repeat EKG within 24 hours. The study drug should be interrupted until the repeat EKG reading. If QTc is still >550 msec than cardiology will be consulted and drug discontinued if abnormality persists.

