10.2 Sample Size Justification

We will describe the distribution of fSAD change within and between treatment groups (n=30 per group) over a 6-month period. Preliminary data suggests that without treatment, fSAD increases 9% on average over a 6-month time period with SD of 9%. If pirfenidone halves this increase over 6 months, we would have a confidence interval for the treatment effect of 4.5+/-4.64%. Power to detect 6-month treatment differences is sensitive to assumptions of the standard deviation above and the ability of pirfenidone to reduce 6-month fSAD progression; a power analysis table is given below for various effect sizes and standard deviations that might be seen in the trial based on a sample size of 60 (30 per group).

	% Increase in FSAD for Pirfenidone Group (vs 9% FSAD increase in Placebo Group)			
Std Dev	0%	2%	4.5%	
5	>99%	>99%	93%	
7	>99%	97%	69%	
9	97%	84%	48%	

We will similarly summarize changes in spirometric parameters and MSC CFU and phenotype over time between and within groups.

While the above power is shown with 60 patients (30 per group), we will plan to enroll 66 patients (33 per group) to account for subject drop out.

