10.3 Primary Endpoint Analysis

We believe the data obtained from our study will provide important radiographic and biological signals regarding the efficacy of pirfenidone. We expect a lower SD as the patient population selected will be much better phenotyped for CLAD presence. The high SD in the preliminary data came from patients who improved over time as this data is derived from patients who had CT scans available as routine care rather than in our study where they will be done prospectively. Furthermore, if fibrotic remodeling by pirfenidone is effective we can potentially even see a decrease in fSAD.

We believe that this CT based novel methodology to evaluate small airway disease will provide us with much stronger signal over 6-month period than FEV1 which reaches a floor effect. So the disease progresses even though FEV1 changes are not very evident ultimately leading to graft failure and death. Furthermore, our ability to isolate mesenchymal cells from BAL offers a first unique scenario to directly study the anti-fibrotic effect of pirfenidone.

This trial will also provide information regarding the tolerance of pirfenidone in a lung transplant population who already take multiple medications with serious possible side effects. Tolerance of pirfenidone in addition to baseline transplant medications will be assessed.

Secondary:

- Change in FEV₁ over 24 weeks by treatment arm (e.g, percent or time weighte)
- Change in FVC over 24 weeks by treatment arm
- Number of subjects with treatment intolerance over 24 weeks
 - Measured by elevated AST, ALT, total bilirubin that results in dose reduction or discontinuing study treatment (the 3 – 5 or greater ULN)
- Number of subjects with Adverse events related to treatment with Pirfenidone
 - Safety of pirfenidone will be measured by adverse events determined to be related to the study drug as determined by the principal investigator through

review of medical history, physical exam and laboratory findings *or be measured by liver and renal function tests, physical exam*

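### The renal exclusion in section 4.4 contradicts itself: its label starts at moderate insufficiency, but its number excludes only creatinine clearance below 15 mL/min

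*Combined protocol and SAP*

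**What the plan says.** The renal criterion is one line in section 4.4: "Moderate to Severe Renal insufficiency (CrCl <15 mL/min calculated by the Cockcroft-Gault equation". It gives a grade in words, then a limit and an equation. The synopsis lists no renal criterion, and no section defines moderate or severe.

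Patients who pass eligibility are treated alike. Section 4.2 states: "Eligible patients will be randomized 1:1 to receive either pirfenidone 801 mg TID or placebo". Section 8 instructs staff to "titrate to the full dosage of 2403 mg/day over a 14-day period as above". Section 8.1 sets numeric action rules for AST and ALT elevation and for QTc, and a reduced dose with ciprofloxacin. It has no renal rule.

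Renal function is watched, without a threshold:
- Creatinine is drawn at screening (5.1), at baseline (5.2) and at each visit through week 24 (5.3 to 5.5). Section 5.3, for example, lists "Safety labs to monitor renal and liver function AP, ALT, AST, total bilirubin, creatinine".
- Section 8.1 says in general terms: "The investigator will monitor patients for toxicities".
- Section 10.3 allows that safety may "be measured by liver and renal function tests, physical exam".
- Section 4.4 lets the principal investigator exclude a patient for any condition judged to preclude participation.
- Section 11.4 has the Safety Officer review laboratory data.

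**The concern.** An eligibility limit set for safety should say one thing. Read by its label, this line turns away patients from moderate impairment downward. Read by its number, it turns away only those with clearance below 15 mL/min. Patients between the two readings are excluded in words and eligible in practice.

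The stakes depend on which half was meant. If the label is the intent, the number lets in patients the authors wanted to keep out. Half of them would start active drug at the full target dose, and only individual judgement could prevent it. If 15 is the intent, the label describes the exclusion as wider than it is. Because staff will follow the number, an error in the number would pass into enrollment and dosing without anyone noticing.

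**Working it through.** The plan gives no derived figure to reproduce. The check is whether the label and the number can describe the same patients.

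**Inputs.** From section 4.4: exclude if CrCl < 15 mL/min by Cockcroft-Gault. Assumed, because the documents give no grades: three conventional band sets. Also assumed: two illustrative patients, a man of 60 years and 70 kg and a woman of 60 years and 60 kg.

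**Step 1. Width of each band that the number admits (CrCl 15 or above).**

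| Assumed bands (mL/min) | Moderate admitted | Severe admitted |
|---|---|---|
| Moderate 30–59, severe 15–29 | 30 of 30 | 15 of 15 |
| Moderate 30–50, severe < 30 | 20 of 20 | 15 of 30 |
| Moderate 30–59, severe < 30 | 30 of 30 | 15 of 30 |

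Under each set all of moderate is admitted, together with CrCl 15–29. That range is half of severe, or all of it if severe starts at 15. The label and the number agree under none of them.

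**Step 2. The same gap in creatinine.** Cockcroft-Gault solved for creatinine is (140 − age) × weight / (72 × CrCl), multiplied by 0.85 for women.

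- Man: 80 × 70 / 72 = 77.78. Dividing by CrCl of 15, 30, 50 and 60 gives 5.19, 2.59, 1.56 and 1.30 mg/dL.
- Woman: 80 × 60 × 0.85 / 72 = 56.67. The same divisions give 3.78, 1.89, 1.13 and 0.94 mg/dL.

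The disputed range (CrCl 15 up to 50 or 60) is therefore about 1.3–1.6 up to 5.2 mg/dL for the man, and about 0.9–1.1 up to 3.8 mg/dL for the woman.

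**Step 3. Two cases.** The man with creatinine 3 mg/dL has CrCl 77.78 / 3 = 25.9. The woman with creatinine 2 mg/dL has CrCl 56.67 / 2 = 28.3. Both are eligible by the number and severe under all three band sets.

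**Step 4. Does other text settle it?** No. Sections 5, 8.1, 10.3 and 11.4 provide measurement and judgement, but none states a renal grade, a second CrCl limit, a renal dose rule or a renal stopping rule.

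**The case against.** The best defence is that the number governs. The line gives one limit, one direction and one equation, and the liver criterion in the same section has the same form of label followed by limits. Two screeners applying it would reach the same decision, and any reader sees the true limit beside the label. The contradiction also depends on bands brought in from outside. Creatinine is followed throughout, and both the principal investigator and the Safety Officer can act on it.

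Much of this stands. The rule can be applied as written, and nobody reading the whole line is misled about the number. But a usable number does not show that it is the intended one, and the mismatch holds under each band set tried. Discretion can remove an individual patient; it does not say which limit was meant.

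A reader might infer more than the documents support:
- *That full-dose pirfenidone is unsafe at CrCl 15–60.* Nothing in the documents shows this.
- *That the number is the misprint.* The label could equally be the error.
- *That a known number of patients is affected.* The documents give no renal distribution for the candidates, so no count can be stated.
- *That the lack of a renal dose or stopping rule is a defect in itself.* The documents do not establish that one is needed. Its absence matters here only because nothing downstream corrects an error in this line.

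**Conclusion.** The point holds as an internal contradiction in an operative safety criterion: one half of the line is wrong as written. Under the assumed bands the gap runs from CrCl 15 up to 50 or 60 mL/min, covering all moderate impairment and the 15–29 range. The exact upper edge depends on the bands chosen; the existence of the gap did not change across the three sets. The creatinine values illustrate two assumed patients and are not estimates for the trial population.

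Confidence is high for the mismatch. No consequence for patients is established. The line should be corrected, but it does not touch sample size, power or the primary analysis.

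**What to change.** Amend the one line in section 4.4 so that label and number agree.

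- **If the label is the intent:** raise the cut-off to the matching limit. Under the assumed bands that is about CrCl < 50 to < 60 mL/min for moderate to severe. If only severe impairment was meant, use about < 30 and drop moderate from the label.
- **If 15 is the intent:** relabel the criterion as kidney failure or end-stage disease, and have the sponsor confirm that 2403 mg/day is acceptable for patients admitted at CrCl 15 and above.

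No new test or visit is needed, because creatinine, weight, sex and date of birth are already collected at screening (5.1). Relabelling costs no recruitment. A higher cut-off may shrink the eligible pool by an unknown amount: the 92 candidates in section 6 are those who "patients meet spirometric criterion for CLAD", with no renal screen mentioned. Before other exclusions, refusals or new cases, that pool could lose 92 − 60 = 32 (35%) and still supply 60 patients. Section 10.2 says "we will plan to enroll 66 patients (33 per group) to account for subject drop out"; for that target it could lose 92 − 66 = 26 (28%). Counting the candidates with CrCl 15–29 and 30–59 before choosing would show the real cost.

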5.0 STUDY VISITS

5.1 Screening

Lung transplant recipients at the University of Michigan will be screened by the study team for participation in this trial. If deemed eligible, subjects will be approached regarding study, and the consent form as well as inclusion and exclusion criteria will be reviewed.

Screening Visit (Performed up to 6 weeks prior to baseline visit and initial study drug dosing) The following procedures will be completed at screening:

- Obtain and document informed consent
- Obtain sex, race, ethnicity, date of birth
- Vital signs (height, weight, temperature, blood pressure, heart rate, respiratory rate, pulse oximetry)
- Review medical history, including transplant history
- Review current medications
- Date of spirometric decline (defined as date of first spirometric measurement used to document spirometric decline) and CLAD phenotype
- Review of bronchoscopy results (if performed in the 6 weeks prior to screening visit)
- Blood draw for screening labs
 - AST, ALT, AP, total bilirubin, creatinine

Screening Bronchoscopy

Bronchoscopy is often employed in routine clinical care to evaluate decline in lung function in lung transplant patients. The University of Michigan (UM) has a standing Institutional Review Board (IRB) approved protocol that that allows for use of BAL fluid for research purposes. If clinical bronchoscopy has been performed within 6 weeks of screening, and no clinical indications of new infection are present (as determined by the principal investigator in consult with the treating pulmonologist), we will utilize the MSC results for this study. If bronchoscopy has not been performed, it may be done following screening and before enrollment, as an

optional part of this study. The informed consent document includes opt in/opt out language for bronchoscopy.

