5.8 Randomization

This is a randomized, double-blind, placebo-controlled multi-center study. Assignment to study treatment will be blinded to the study subjects, investigational site personnel, study vendors, and the Sponsor study team, except for the delegated personnel who will review and check the randomization and drug allocation for accuracy.

All patients will be randomized at the Baseline visit, using stratified block randomization with undisclosed block sizes. The stratification factor is FEV1 first vs concurrent FEV1 and FVC decline at time of CLAD onset. Our statistician, [name], will assist with randomization. She will provide the Research Pharmacy (via email) with randomization codes for two separate strata as mentioned above. Within each stratum the statistician will indicate treatment assignment"Active Pirfenidone" or "Placebo" and treatment label ID number. The Research Pharmacist (RP) will be told upon patient entry the stratum to which the patient belongs, identifying the appropriate randomization list for each patient. The RP will then dispense Active or Placebo based on the randomization code on the randomization list. The RP will refer to the randomization code at each dispensing.

In the event of a medical emergency in which breaking the blind is required to provide medical care to the subject, the investigator may obtain treatment assignment directly from the study statistician for that subject.

Visit	Screening ^A	1 Baseline	2 ^B +/- 7days	3 ^B +/- 7days	4 +/- 14day	5 ^B +/- 7days	6 ^B +/- 7days	7 EOT +/-	8 EOS +/-
					S			14day s	7days
Week	-6 - 0	0	4	8	12	16	20	24	28 ^c
Inclusion/exclusion criteria	х								
Informed consent	Х								
Randomization		Х							
Demographics	Х								
Vital Signs	Х	Х			Х			х	
Physical exam	Х	Х			Х			х	
Medical history	х	х							
Adverse events	х	х	Х	х	х	х	х	х	х
Non-elective hospitalizations		х	x	x	x	х	х	х	x
Medication Compliance			Х	х	х	х	х	х	
Concomitant medications	X	x	х	x	x	х	x	х	
Pregnancy test ^D		Х							
Standard of care labs	x	x	х	х	х	х	х	х	
including									
immunosuppressive									
drug levels									
Safety labs (LFTs) ^F	Х	Х	Х	Х	Х	Х	Х	Х	
Spirometry	Х				Х				
Full PFTs		Х						Х	
HRCT ^G		Х						Х	
EKG		Х			Х			Х	
Bronchoscopy with BAL ^H	x	x						х	
Vital status assessment									х

Table 1. Schedule of Assessments

A The time period between the screening and enrollment visit may be up to 6 weeks

B Weeks 4, 8, 16, 20: Laboratory testing may be performed locally

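### Time since CLAD onset is obtainable from screening data and bears on the protocol's reason for broad enrolment, but no planned analysis uses it

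*Combined protocol and SAP*

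**What the plan says.** **Who may enter.** Section 4.3 requires a spirometric diagnosis of CLAD, and neither 4.3 nor 4.4 limits the time since onset. Section 6 states "The study plans to include all patients with diagnosis of CLAD irrespective of the stage". The feasibility count there is of prevalent cases, 92 of them, found "At present among all alive patients with lung transplant at our center". The same section says that "CLAD becomes a chronic disease and patients can survive for prolonged periods of time after onset of CLAD".

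**Why entry is broad.** The paragraph in section 6 ends: "Hence, the ability of an antifibrotic agent to halt fibroproliferation at various time points after onset of CLAD is of key significance".

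**What is recorded.** The screening list in 5.1 includes "Date of spirometric decline (defined as date of first spirometric measurement used to document spirometric decline) and CLAD phenotype".

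**What is used.** Section 5.8: "The stratification factor is FEV1 first vs concurrent FEV1 and FVC decline at time of CLAD onset". This uses the pattern of decline at onset, not the time elapsed since. Sections 10.1 to 10.3 and the synopsis compare change by treatment arm and name no covariate, subgroup or interaction. Section 10.2 plans with one untreated mean and a common SD: "Preliminary data suggests that without treatment, fSAD increases 9% on average over a 6-month time period with SD of 9"%. The power table also tries SDs of 5 and 7.

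**The concern.** The trial can mix patients whose lung function fell recently with patients who have lived with CLAD for a long time. If untreated progression depends on that duration, its contribution to the spread of fSAD, FEV1 and FVC change stays in the error term, although a pre-randomisation variable that could remove it is already collected. Precision is scarce here: at the SD seen in the preliminary data, the plan's own table gives 48% power for a halving of progression.

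The second part concerns interpretation. Section 6 enrols all durations partly because an effect at different times after onset matters, yet nothing in section 10 would describe whether the effect looks similar in early and late disease. An analysis of this kind chosen after unblinding would carry much less weight than one written down beforehand.

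**Working it through.** **Inputs from section 10.2:** 30 per group, SD 9, untreated rise 9, treated rise 4.5, so a difference of 4.5. Alpha is not stated; two-sided 0.05 is assumed, and it reproduces the table.

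**Inputs assumed:** the share of variance in fSAD change explained by time since onset, R², from 0 to 0.30. The documents give neither the spread of durations nor their relation to fSAD change.

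**1. The plan's own figures.** Standard error = 9 × √(2/30) = 9 × 0.2582 = 2.324. Half-width = t(58 df) × 2.324 = 2.002 × 2.324 = 4.65, against 4.64 stated. Noncentral t power for 4.5 is 47.8%, against 48% stated. The other eight cells of the table also agree to rounding. One common mean and SD therefore account for the whole table, and duration plays no part in it.

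**2. Adjusting for duration.** Residual SD = 9 × √(1 − R²). Half-width = t(57 df) × residual SD × 0.2582, with t = 2.002.

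| R² | Residual SD | 95% half-width | Power for 4.5 |
|---|---|---|---|
| 0 | 9.00 | 4.65 | 48% |
| 0.05 | 8.77 | 4.54 | 50% |
| 0.10 | 8.54 | 4.41 | 52% |
| 0.20 | 8.05 | 4.16 | 57% |
| 0.30 | 7.53 | 3.89 | 62% |

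The R² = 0 row shows the price if duration turns out to be irrelevant: power remains 47.8%.

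**3. Chance imbalance.** The standardised difference in mean duration between arms has SD √(2/30) = 0.258. The probability that it exceeds 0.5 in either direction is that of |z| > 0.5/0.258 = 1.94, about 5.3%. An imbalance of 0.5 SD shifts the unadjusted estimate by 0.5 × r × 9, where r = √R²:

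- R² = 0.05: r = 0.22, shift = 1.0 point
- R² = 0.30: r = 0.55, shift = 2.5 points

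This variation is already contained in the 4.65 half-width. It is another way of seeing the same imprecision, not an additional cost.

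**4. What an effect-by-duration estimate could show.** Split each arm into early and late halves of 15. The difference between the two treatment effects has standard error 9 × √(4/15) = 4.648. Its 95% half-width is 2.003 × 4.648 = 9.3 points, about twice the target effect. Power to detect a 4.5-point difference between halves is about 16% (normal approximation).

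**The case against.** **The section 6 sentence is not an objective.** It concludes an argument for broad eligibility. The aims and the endpoint lists ask no effect-by-duration question, and a pooled estimate in a mixed population is consistent with that argument. This stands: the plan has not failed to address a formal aim.

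**Nothing shows that duration is prognostic.** A reader might infer that it must be, because 9 points in six months is 18 a year and would fill the lung in 100/18 = 5.6 years, while patients are said to survive for long periods. The documents do not support that step. The unit of the 9% is not given, and the length of survival is not quantified. Other explanations fit as well, such as differences between patients unrelated to duration, selective loss of fast progressors, or a ceiling tied to baseline fSAD. Section 10.3 attributes the large preliminary SD to patients who improved and does not mention duration.

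**The plan does not say that progression is equal.** A reader might take the single planning mean as a claim that new and old CLAD progress alike. That is an inference; an SD of 9 leaves ample room for differences between patients.

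**The onset record is not idle.** The stratum depends on the pattern of decline at onset, so onset has to be identified in any case. Only elapsed time goes unused.

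**The gap belongs to a larger one.** Section 10.3 names no model at all, not even with the stratification factor or baseline fSAD. That is correct, but supplying a model would not by itself bring in time since onset.

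**A subgroup test would be hopeless at this size.** Agreed, which is why only a descriptive estimate is suggested.

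**Conclusion.** The point holds as an inexpensive improvement rather than as a flaw in validity. CLAD of any duration may enter, the onset date is collected, and elapsed time appears in neither the stratification nor the analysis. The pooled comparison remains unbiased under randomisation.

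The gain in precision ranges from nothing to a half-width of 3.89 and 62% power. It depends entirely on the assumed 0% to 30% of variance explained, together with SD 9, 30 analysed per arm and two-sided 0.05. At the low end (5%) the gain is only about two percentage points of power. What does not depend on that assumption is that no estimate across disease duration is planned, although section 6 gives effect at different times after onset as a reason for enrolling so widely. The actual spread of durations in the recruitment pool cannot be seen in the available text.

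**What to change.** In section 10.3:

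- Prespecify time from the 5.1 date of spirometric decline to baseline, continuous and on the log scale, as a covariate in the arm comparisons of fSAD, FEV1 and FVC change. Enter it alongside the stratification factor and the baseline value of the outcome.
- Add a descriptive estimate, with 95% CI, of how the treatment effect varies with that continuous variable. Label it exploratory, and state its imprecision in advance (an early-versus-late contrast has a half-width of about 9.3 points at SD 9).
- Tabulate time since onset by arm at baseline.

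The duration term costs one degree of freedom in each main model. The rest is analysis-plan wording, with no new visits, data or patients. It should be settled before unblinding so that the choice of covariate cannot appear data-driven.
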